Study Title: Effects of Interleukin (IL)- 4R-alpha Inhibition on Respiratory Microbiome and Immunologic Correlates in Severe Asthma

PI: [name]

NCT: NCT05036733

Protocol Version IRB Approval Date: 9/8/2021

Effects of IL-4 α Inhibition On The Respiratory Microbiome And Immunologic Correlates In Patients With Severe Asthma: A Pilot Study

Principal Investigator: [name]; UM Division of Pulmonary/Critical Care Med

Co-Principal Investigator: [name] MD; UM Division of Allergy/Clinical Immunology

Co-Investigator: [name]; UM Division of Pulmonary/Critical Care Med

I. Overview

This prospective pilot study will address the following main research question: *“Does IL-4Ra (dupilumab) inhibition of Type 2-mediated immune responses alter the respiratory microbiome within a 4 month period of treatment initiation and follow up, and if so, what are the specific microbiological changes and immune response correlates of these changes?”* We will compare pre- and post-dupilumab effects on the microbiomes, immune responses and metabolome of severe asthma patients who are clinically eligible for dupilumab treatment. Eligible patients will be screened and enrolled prior to start of therapy and return for visits at 1 month and 4 months after initiation of treatment. The overall goal of this study is to understand biological responses related to dupilumab treatment among severe asthma patients who have clinical indication to be treated. We will collect biospecimens (nasal, sputum, stool, blood) to examine dupilumab-related changes in the microbiome, measured immune responses, and clinical outcome measures. Research methods will include microbiome profiling of respiratory and stool samples, cytokine measurements from nasal epithelial lining fluid, and metabolite analysis of stool samples.

II. Background

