Inhibition of the IL-4 receptor α (IL-4Ra) by dupilumab has been shown to significantly improve clinical outcomes and disease severity measures in Type 2 (T2)-driven phenotypes of severe asthma, as well as atopic dermatitis (AD), and chronic rhinosinusitis with nasal polyposis (CRSwNP) [1-4]. These findings are accompanied by demonstration of dupilumab-induced suppression of T2-related allergic responses, both in the blood and in organ-specific compartments such as lesional AD skin and nasal samples in CRSwNP. These include measures of total IgE, TARC, and eotaxin-3 [5,6], and of nasal polyp tissue levels of the same plus eosinophilic cationic protein and PARC (CCL18) [4]. Gene expression analysis of lesional AD skin identified congruent findings with Th2-associated mediators, but also decreased expression of genes involved in other immune cell pathways, such as dendritic cells and Th17 cells [6]. Thus, biomarkers of effective suppression of T2-related immune responses are evident both systemically and in affected tissue compartments. Further analyses of the latter may reveal localized interactions that contribute to differences between severe asthma patients in disease phenotype and therapeutic response. Indeed, despite recent advancements in anti-T2 directed therapies, not all severe asthma patients clinically respond to such treatments. Thus, more research to understand this is needed, as was noted in a recent NEJM editorial [7].

Published data on changes in airway immune responses with dupilumab treatment are sparse, but similar suppression of T2-mediated inflammation would be expected. Although T2-high inflammation plays a key role in many with poorly controlled asthma, at the same time the potential ramifications of long-term suppression of T2-related immune responses are uncertain, particularly

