Dupilumab-eligible severe asthma patients will be identified and recruited from asthma and allergy clinics at the University of Michigan. Severe asthma patients are seen and cared for by Pulmonary and Allergy faculty at two main outpatient clinic locations. All severe asthma patients who meet clinical prescribing criteria for dupilumab are considered eligible and will be recruited for this study. The study coordinator and/or physician investigator will meet with subjects to provide information about the study and invite them to participate in this 3-visit study occurring over a 4-month period. We will enroll 15 severe asthma patients who complete all 3 visits. The funder of the grant for this project (Regeneron) will provide dupilumab for this study.

Inclusion criteria:

1. Adults ages 18 or older with physician-diagnosed/-managed severe asthma who are clinically eligible for dupilumab (clinical criteria below).
2. Current treatment with a medium-to-high-dose inhaled glucocorticoid (fluticasone propionate at a total daily dose of ≥ 440 μ g or equipotent equivalent) plus up to at least one additional controller (e.g., a long-acting β 2-agonist or leukotriene receptor antagonist)
3. Eosinophilic asthma phenotype (blood eosinophil level >300) or asthma requiring daily oral corticosteroids
4. Asthma that is uncontrolled, as defined by a score on the Asthma Control Test of 19 or lower, OR a worsening of asthma in the past year that led to an asthma hospitalization, ED visit, or 3 days of oral corticosteroids
5. Severity of asthma that, in the opinion of the subject's asthma care specialist, requires dupilumab for control

Exclusion Criteria:

1. Patients with diagnosis of other chronic lung diseases (e.g. COPD, idiopathic pulmonary fibrosis, Churg-Strauss syndrome, ABPA, etc.)

2. Current smoker or reported smoking within 1 month of the screening visit (tobacco or any inhaled recreational product)
3. Greater than 10 total pack-year of cigarette smoking history
4. Treatment with oral corticosteroids for an asthma exacerbation 1 month prior to screening or during the screening period
5. Use of any biologic therapy for asthma within the past 3 months
6. Respiratory or GI illness within 1 month prior to screening or during the screening period
7. Treatment with antibiotics for acute infections within six weeks prior to screening or during the screening period.
8. Pregnancy at enrollment or during the study
9. Known hypersensitivity to dupilumab or its excipients

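### Exclusion 5 limits the biologic washout to drugs taken for asthma, so a patient recently treated with a Type 2-directed biologic for another disease could enter without an untreated baseline

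*Combined protocol and SAP*

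**What the plan says.** Exclusion 5 in section IV reads "Use of any biologic therapy for asthma within the past 3 months". No other criterion mentions biologics, apart from known hypersensitivity to dupilumab (exclusion 9).

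Section II (Background) names atopic dermatitis and chronic rhinosinusitis with nasal polyposis as further Type 2 diseases in which dupilumab improves outcomes. It concludes that "biomarkers of effective suppression of T2-related immune responses are evident both systemically and in affected tissue compartments". The same section reports the team's own finding that airway bacterial burden is lower where Type 2 airway inflammation is higher.

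The Overview states the design: "We will compare pre- and post-dupilumab effects on the microbiomes, immune responses and metabolome of severe asthma patients". There is no comparator arm. It also says "Eligible patients will be screened and enrolled prior to start of therapy", and Table 1 shows no drug at screening and drug start at Visit 1. Section XII tests Hypothesis 1 by paired comparison of baseline with month 1 and with month 4.

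**The concern.** The purpose of a biologic washout here is to obtain a baseline that is free of Type 2 suppression by an earlier drug. That depends on which drug was given and when, not on the disease that prompted the prescription. A restriction by indication lets through an exposure that, on the Background's own account, acts systemically and also in nasal tissue. Nasal samples are a source for the primary endpoint.

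In an exposed patient, the change from Visit 1 would mix the start of dupilumab with carry-over from, or loss of, an earlier treatment. No concurrent control can separate the two. Hypotheses 1 and 2 rest directly on that change, and Hypotheses 3 and 4 relate changes to one another, so they inherit the same baseline.

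**Working it through.** **Step 1. Does anything else in the protocol close the gap?**

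| Possible guard | What it stops | What it leaves open |
|---|---|---|
| Enrolment before therapy (Overview); no drug at screening (Table 1) | A current dupilumab user | Dupilumab recently stopped; any other biologic, recent or continuing |
| Inclusion 3: blood eosinophils above 300, or daily oral corticosteroids | Some patients with suppressed eosinophils | The count carries no date, and the corticosteroid route needs no count |
| Inclusion 4: ACT of 19 or lower, or a worsening in the past year | Patients whose asthma is controlled | A past-year event may predate the other biologic |
| Inclusion 5: specialist judges that dupilumab is required | Patients with no asthma need for it | Says nothing about earlier treatment |
| Screening questions by phone or email (section V) | Whatever the criteria name | Exclusion 5 names only asthma use; Table 1 has no blood test at screening |
| Full history, blood count, FeNO and NELF at Visit 1 | May reveal exposure or a suppressed baseline | No eligibility rule would then exclude the patient |
| Fixed effects in the Hypothesis 3 models (section XII) | Names corticosteroids and macrolides among chronic treatments | Prior biologics are not named, and the paired tests for Hypothesis 1 carry no covariates |

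The guards narrow the gap. None of them closes it.

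**Step 2. Dilution of the mean change.** Input: 15 completers (section IV). Assumptions: k exposed patients, and a fraction r of the full change still to come in each.

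Mean change retained = (15 − k + r·k)/15, so the loss is k(1 − r)/15.

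- r = 0 (no further change): 1/15 = 6.7%, 2/15 = 13.3%, 3/15 = 20%.
- r = 0.5 (half the change): 0.5/15 = 3.3%, 1/15 = 6.7%, 1.5/15 = 10%.

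**Step 3. Illustration in terms of power.** The protocol gives no sample size calculation, alpha, effect size or SD, so there is no planned figure to reproduce. Assumptions: paired t-test, n = 15, two-sided alpha 0.05, and the same SD of change in exposed and unexposed patients. By the noncentral t distribution, 80% power then needs a standardised change d of about 0.78. Simulated power (100,000 runs per case) with r = 0:

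| d | k = 0 | k = 1 | k = 2 | k = 3 |
|---|---|---|---|---|
| 0.50 | 44% | 39% | 34% | 29% |
| 0.78 | 80% | 73% | 65% | 57% |
| 1.00 | 95% | 91% | 85% | 77% |

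With r = 0.5 and d = 0.78, the values for k = 1, 2 and 3 are 77%, 74% and 70%.

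These figures describe dilution only. If a patient's earlier drug is wearing off over the same months, the distortion could go in either direction, and the documents give no basis for sizing it.

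**The case against.** The case against has substance on several points.

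**Such patients may be few.** To enter, a patient must have raised eosinophils or need daily oral corticosteroids, have uncontrolled asthma, and be judged to need dupilumab. Someone who meets all of that is not obviously suppressed. This stands: a reader might infer that exposed patients will enrol, or that each arrives already suppressed, and the documents support neither. Carry-over depends on the agent and the last dose. Collecting the SNOT-22 shows interest in sinus symptoms and says nothing about how often biologics have been used.

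**The current dupilumab user is already excluded.** This also stands. What remains is the recent ex-user and the user of another agent.

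**The window is not left open during screening.** A reader might note that exclusions 4, 6 and 7 add the screening period, as in "Treatment with antibiotics for acute infections within six weeks prior to screening or during the screening period", and infer that exclusion 5 leaves those weeks uncovered. Those criteria count back from screening and need the addition. Exclusion 5 looks back from an unstated date, and all criteria are reviewed in full at Visit 1, 2 to 4 weeks after screening. Applied there, it already covers the screening period. Only the missing anchor date deserves attention.

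**The wording has a second reading.** The phrase could mean the class of asthma biologics, whatever prompted the prescription. That is possible, but a coordinator working from a short question list could reasonably take it as use for asthma. The ambiguity is itself a reason to clarify.

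**Exposure would probably come to light.** The Visit 1 history and baseline markers may show it, and the covariate list is not exhaustive. But no rule says what to do with such a patient, and agent and last-dose date are not required data.

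**Conclusion.** The gap is present in the text. The biologic washout depends on indication, and no other provision bars a recent Type 2-directed biologic taken for another disease. Such a patient could enter, and the single-arm comparison would then lack an untreated baseline for that patient.

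The size is unknown. The k/15 dilution is arithmetic on an assumed number of patients and an assumed absence of further change. The power figures also assume an alpha, an effect size and a common SD. They show only that one to three patients out of 15 would not be negligible. That carry-over would shift the baseline microbiota is plausible from the Background's link between Type 2 status and bacterial burden, but it is not established. It is close to the question that the pilot asks.

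In an exploratory pilot this is of minor to moderate importance. It is a cheap improvement and does not invalidate the design.

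**What to change.** Keep the protocol's own 3-month window and reword exclusion 5 along these lines: *use, within the 3 months before Visit 1, of any biologic that acts on Type 2 inflammation (including dupilumab), whatever the indication*. Counting back from Visit 1 ties the window to the baseline sample and supplies the missing anchor. Barring every monoclonal antibody would go further than the rationale, which concerns Type 2 carry-over only.

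At screening and again at Visit 1, record any prior biologic use: agent, indication and date of last dose. In section XII, state that the primary paired comparisons will be repeated without any exposed patient, and that the two sets of estimates will be compared. This covers exposure that comes to light late and anyone enrolled under the present wording.

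The cost is one reworded line, one screening question, a few data fields and one repeat of planned analyses. The downside is an occasional lost candidate, and a sensitivity analysis on fewer than 15 patients will be imprecise.

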- To determine changes in the respiratory microbiome after inhibition of IL-4R α in patients with asthma at 1 and 4 months after initiation of treatment

Primary Endpoint (Biological) Measures

- Changes in measured features of respiratory microbiota composition (bacteria, fungi), profiled from induced sputum and nasal samples. Such features include alpha- and beta-diversity ecologic measures, which reflect microbiota composition within and between-samples, respectively. Examples include Shannon and phylogenetic diversity indices, richness and evenness metrics (alpha-diversity), and Unifrac or Bray-Curtis distance measures to compare across samples (beta-diversity). Additional readouts of the microbiome to be analyzed include bacterial burden by quantitative PCR, abundance profiles of microbial community members, and microbial gene functions annotated from metagenomic sequence data.
- Changes in similarly calculated measures of microbiota composition in stool samples collected before and after dupilumab initiation (baseline and 4 months)

Secondary Objectives

- To examine correlations between changes in measured features of the respiratory microbiome and changes in blood and airway immune responses with dupilumab treatment
- To determine relationships between changes in measured features of the respiratory microbiome and changes in clinical outcome measures including lung function and asthma control scores with dupilumab treatment
- To determine if combinations of correlated immune markers and microbiota patterns predict improvement or lack of improvement in clinical outcome measures related to dupilumab treatment
- To explore associations between gut microbiome composition, aeroallergen sensitization, severe asthma features and response to dupilumab treatment.
- To explore the relationship between gut microbiota compositional, the intestinal metabolome, and response to dupilumab.
- To explore and compare dupilumab-related, compartment-specific changes in the respiratory microbiome to that observed in the gut microbiome

Secondary Endpoint (Clinical) Measures

Clinical outcome measures (all visits)

- Spirometry: FEV1/FVC ratio, FEV1, and FVC pre- and post-bronchodilator.
- Fractional exhaled nitric oxide (FeNO)
- Asthma Control Test [16]
- Asthma quality of life questionnaire (mini-AQLQ) [17]
- SNOT-22 [18, 19]
- Asthma medication use and dosage
- Asthma exacerbations requiring at least 3 days of oral corticosteroids

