Immune and Other Microbial Biomarkers - blood, induced sputum, nasal epithelial lining fluid (NELF), stool, exhaled air

- Serum total IgE and specific IgE to aeroallergen panel (ImmunoCap)
- Complete blood count with cell differential
- Sputum cell differential counts
- Sputum, NELF cytokines (Mesoscale Discovery; 30-plex panel: Eotaxin, Eotaxin-3, GM-CSF, IFN- γ , IL-10, IL-12/IL-23p40, IL-12p70, IL-13, IL-15, IL-16, IL-17A, IL-1 α , IL-1 β , IL-2, IL-4, IL-5, IL-6, IL-7, IL-8, IL-8 (HA), IP-10, MCP-1, MCP-4, MDC, MIP-1 α , MIP-1 β , TARC, TNF- α , TNF- β , VEGF-A)
- Sputum antimicrobial peptide expression (RT-PCR): defensins, lysozyme, lactoferrin, LL-37, and secretory leukocyte protease inhibitor
- Total bacterial burden in sputum samples by 16S rRNA Q-PCR or droplet digital PCR; with determination of both relative and absolute abundances of taxa.
- Respiratory microbial functional gene annotations from metagenomic sequencing
- Fecal metabolites by global/untargeted and targeted short-chain fatty acid assays

Primary hypotheses:

Hypothesis 1. Dupilumab-induced suppression of T2 inflammation in severe asthma is associated with changes in respiratory tract bacterial burden at 1 month and 4 months after treatment initiation (16S rRNA qPCR of bacterial DNA in induced sputum)

Hypothesis 2. Dupilumab-induced suppression of T2 inflammation in severe asthma is associated with changes in the compositional structure of respiratory and/or gut microbiota, detectable at 1 month and 4 months after initiation of treatment. (bacterial and fungal microbiota profiles and related measures of microbial diversity in induced sputum and stool)

Hypothesis 3. Dupilumab-induced changes in specific biomarkers (e.g. T2 and non-T2-related cytokines; targeted gene expression) correlate with changes in the respiratory and/or gut microbiome (phylogenetic diversity, specific compositional and functional profiles)

Hypothesis 4. Dupilumab-related improvement or lack of improvement in clinical outcomes (lung function, asthma control scores) over a 4-month period are associated with changes in specific characteristics of the respiratory and/or gut microbiome.

IV. STUDY OVERVIEW, INCLUSION/EXCLUSION CRITERIA, PROCEDURES

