2 Per current policy (as of Jan 2021) at Michigan Medicine, subjects must undergo COVID-19 testing (nasal swab) and have a negative test within 96 hrs prior to aerosol-generating procedures. Testing will be arranged by study team for each visit. If the test is positive for COVID-19 or test result is not available, the study visit will need to be rescheduled.

3 A physician must see the subject at each visit.

4 FeNO measurement and NELF collection should be performed before spirometry and sputum induction.

5 Brief telephone call by study coordinator to (a) ensure subjects are self-administering dupilumab doses between study visits, (b) address any interim questions, and (c) remind them of upcoming in-person study visit. The TC encounters are important to maintain contact with subjects and ensure adherence and follow through during the course of the study

V. VISIT-SPECIFIC DETAILS

SCREENING.

This is the first encounter with eligible patient at which time information about the study is provided by the study coordinator. This may occur by phone or email. A short list of questions will be asked to confirm eligibility. If on the basis of this screen, an individual is eligible to participate the study, a copy of the informed consent will be provided for subject review prior to Visit 1. Signed informed consent will be collected at Visit 1. (*Anticipated total time by study coordinator: 10 minutes.*)

VISIT 1.

Preparations

1. V1 should be scheduled within 2-4 weeks after screening. Subjects will be reminded by study coordinator to take their usual asthma treatments as prescribed including on the day of the visit. Coordinate V1 scheduling with physician investigator availability to perform history and physical exam.
2. Coordinate with Research Pharmacy preparation of dupilumab syringe for administration to subjects after completing all visit testing. Ensure appropriate orders are submitted in advance of V1 date. Also ensure subject will have subsequent doses of dupilimab prepared for self-administration at home between V1 and V2.
3. Notify [name] in [name] Lab ([name]) the day before the visit so that the lab can prepare necessary materials to collect and process samples. Ensure a bucket of ice is available to place collected samples for transport to [name] lab.

Visit procedures

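### Exclusion 7 covers only antibiotics for acute infections, so a recently stopped antifungal or non-acute antibiotic is not barred, although fungi are in the primary endpoint

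*Combined protocol and SAP*

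**What the plan says.** Section IV, Exclusion Criteria, item 7 excludes "Treatment with antibiotics for acute infections within six weeks prior to screening or during the screening period". It is the only criterion that concerns antimicrobial drugs. The term antibiotics is not defined, and antifungals are not mentioned in the eligibility, concomitant-medication or analysis text.

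The endpoint is wider than that exclusion. Section III, Primary Endpoint (Biological) Measures, lists "Changes in measured features of respiratory microbiota composition (bacteria, fungi), profiled from induced sputum and nasal samples". Hypothesis 2 covers "bacterial and fungal microbiota profiles and related measures of microbial diversity in induced sputum and stool".

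Eligibility is open by default: "All severe asthma patients who meet clinical prescribing criteria for dupilumab are considered eligible and will be recruited for this study". Two other exclusions bear on the point. Item 1 removes other chronic lung diseases, including ABPA. Item 6 removes "Respiratory or GI illness within 1 month prior to screening or during the screening period".

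On timing, Section V, Visit 1, Preparations, states "V1 should be scheduled within 2-4 weeks after screening". On design, Section I states "We will compare pre- and post-dupilumab effects on the microbiomes, immune responses and metabolome of severe asthma patients", and Table 1 gives one pre-treatment sampling visit. In Section XII, the Hypothesis 1 and 2 comparisons name no medication covariate. Corticosteroids and macrolides appear as fixed effects only in the Hypothesis 3 mixed models, which are reused for Hypothesis 4.

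**The concern.** Exclusion 7 shows that the authors regard carry-over from antimicrobials as a threat to the baseline. As worded, it protects the bacterial readouts against one class of use and gives the fungal readouts no protection of their own.

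Two kinds of patient pass the rule when it is applied as written. One recently finished an antifungal course. The other recently finished an antibiotic given for something other than an acute infection, for example procedural prophylaxis. In either case the Visit 1 sample may be depleted. If the community regrows by month 1 or month 4, the paired difference contains a recovery unrelated to dupilumab. No concurrent control arm or second baseline sample is available to separate the two.

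The exposure is plausible here, because Inclusion 2 requires medium-to-high-dose inhaled steroid and Inclusion 3 admits patients on daily oral steroid. At stake are the fungal part of Hypothesis 2 and, for non-acute antibiotics, the bacterial burden comparison of Hypothesis 1 and the bacterial part of Hypothesis 2.

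**Working it through.** The plan states no alpha, power, effect size or SD, and gives 15 without a calculation (Section XII says that none was possible). There is no figure of its own to reproduce. The check has three parts.

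**1. Drug-free interval at Visit 1.** Inputs: six weeks before screening (Exclusion 7), and 2 to 4 weeks from screening to Visit 1 (Section V), with the screening period taken to run to Visit 1.
- Antibiotic for an acute infection: at least 6 + 2 = 8 to 6 + 4 = 10 weeks.
- Antifungal: no required interval, 0 weeks.
- Antibiotic for a non-acute reason: no required interval, 0 weeks.

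**2. How many patients could be affected.** The documents give no rate, so these are assumptions. With n = 15 and rate p, the expected number is 15p, P(at least one) = 1 − (1 − p)^15, and P(at least two) = 1 − (1 − p)^15 − 15p(1 − p)^14.

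| Assumed p | Expected | At least one | At least two |
|---|---|---|---|
| 2.5% | 0.375 | 32% | 5% |
| 5% | 0.75 | 54% | 17% |
| 7.5% | 1.125 | 69% | 31% |
| 15% | 2.25 | 91% | 68% |

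The rate must be read per endpoint. On the mechanism proposed, antifungals depress fungi and antibiotics depress bacteria. If 5% to 15% is the combined rate and it splits evenly (a further assumption), each endpoint faces 2.5% to 7.5%.

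**3. Effect on a paired comparison.** Suppose k of 15 patients carry a rebound of s, in SDs of the within-patient change, all in the same direction and with no drug effect. The mean change shifts by k × s / 15. The rejection rate is that of a simulated two-sided 5% paired t-test with normal changes.

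| k | s | Mean shift (SD) | Rejection rate |
|---|---|---|---|
| 1 | 0.5 to 1 | 0.03 to 0.07 | about 5% |
| 1 | 2 to 3 | 0.13 to 0.20 | about 4% to 5% |
| 2 | 0.5 to 1 | 0.07 to 0.13 | about 5% to 6% |
| 2 | 2 to 3 | 0.27 to 0.40 | about 8% to 9% |
| 3 | 2 | 0.40 | about 14% |

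One affected patient does not raise the error, because the outlying change inflates the SD along with the mean. When the number affected is allowed to vary at random, with s of 2 to 3, the error is about 5% at p = 2.5%, about 7% at p = 7.5%, and 12% to 16% only at p = 15% on a single endpoint.

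For scale, a paired t-test with n = 15 has 80% power at two-sided 5% for a mean change of 0.78 SD. Two patients shifted by 2 to 3 SD would contribute 0.27/0.78 to 0.40/0.78 of that, about 34% to 51%.

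**The case against.** A reader might infer that patients on antifungals enter freely and that their recovery will be reported as a dupilumab effect. The documents do not support that. Exclusion 1 (ABPA) and Exclusion 6 (recent respiratory or GI illness) remove some likely users. A physician takes a full history at Visit 1 (Section VI, item 1) and may learn of the exposure. A patient on a stable antifungal throughout has no recovery to misread, and one who starts a course after Visit 1 biases the comparison the other way. The problem needs a course stopped shortly before baseline, followed by regrowth. A broad reading of antibiotics could also include antifungals given for acute infection, although that is not the ordinary meaning.

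A reader might also infer a serious inflation of error from the high chance of at least one exposed patient. That does not follow. One patient in 15 leaves the test at its nominal level; inflation needs two or more with large shifts in the same direction. A rebound of 2 to 3 SD has no support in the documents. Section XII calls the study a proof-of-concept pilot with exploratory hypotheses, so no confirmatory error rate is at risk.

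Nor is the damage beyond repair. The oral rinse and tongue scraping taken before each sputum induction (Section VI, item 11) could reveal a disturbance confined to the mouth, such as treated thrush. Exposed patients could be left out of a sensitivity analysis if their exposure is recorded.

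These points limit the size but do not close the gap. Exclusions 1 and 6 miss other indications, and illness that ended more than a month before screening. The Visit 1 history has no rule to apply to an antifungal it uncovers. The oral control mitigates one scenario only, and the plan specifies no sensitivity analysis.

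**Conclusion.** The gap is in the text. The exclusion does not match an endpoint that includes fungi, and a patient whose baseline follows soon after a stopped antifungal or non-acute antibiotic can enter unless Exclusion 1 or 6 happens to apply. In an uncontrolled before/after study with one baseline sample, regrowth in such a patient could be mistaken for a dupilumab-related change.

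The likely effect on any single comparison is modest. With one affected patient the mean change is biased but the error rate is not raised. Two patients with large rebounds bring the error to about 8% to 9%, and two with small rebounds to about 5% to 6%. These figures rest on an assumed exposure rate, rebound size and common direction, none of which the documents give. Taxon-level fungal results may be more exposed, since few patients may carry a given taxon; that was not quantified. The change is worth making because it is cheap and protects a named part of the primary endpoint.

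**What to change.** 1. Reword Exclusion 7 so that its existing window (six weeks before screening, and the screening period) covers antibacterial and antifungal treatment for any indication, by any route that reaches the sampled sites: systemic, inhaled, oral-topical, intranasal or sinus. The nasal routes matter because nasal samples are in the endpoint.
2. Except a chronic maintenance macrolide only if its use has been stable over that same window. This keeps the patients for whom Section XII plans macrolide adjustment, without admitting one who has just started.
3. Ask about these drugs by class at screening and at Visit 1.
4. Record antimicrobial exposure, with dates, through Visit 3. Section IX allows medication for intercurrent illness and documents it, but no analysis rule uses that record.
5. Pre-specify a sensitivity analysis of the Hypothesis 1 and 2 comparisons without exposed patients.

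Cost: one reworded criterion, added medication questions and one extra analysis. Some otherwise eligible patients would enter later or not at all, a small cost but a noticeable one when only 15 are sought. If enrolment is already complete, collecting exposure retrospectively and running step 5 would address the point in part.
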